5.2.3 Validation of Self-Reported Events

A self-administered questionnaire used by study participants at short intervals is a sensitive tool which captures almost all serious clinical outcomes [8]. From a methodological point of view, it captures a much higher proportion of these outcomes than methods relying only on the prescribing HCP who may not be involved in the diagnosis and treatment of these outcomes. However, there is a significant difference between the rates of patient-reported and medically confirmed events after validation as laypersons often misclassify adverse events, therefore, assessment of the self-reported events is of utmost importance.

In this study, self-reported events considered as a defined primary outcome, i.e., major malformations defined in section 5.3.1 will be validated with the goal to identify if the reported event was medically confirmed.

The follow-up questionnaires (ePRO) will be programmed with specific constraints allowing for additional questions to be displayed if a potential major malformation is reported by a study participant. Questionnaires with a potential major malformation are automatically flagged and transferred to the medical event validation team at ZEG Berlin. The medical event validation team will work within the EDC solution to validate all events considered as a primary study outcome. During the validation process it may be necessary to re-contact the study participant or diagnosing and/or treating HCP for validation of the information initially received from the study participant to, a) clarify information and b) obtain additional information for medical confirmation of the event. All additional data gathered during this procedure is entered into the eCRF EDC solution by ZEG Berlin. Further details will be described in the Data Management Working Procedures.

ZEG Berlin will oversee the outcome validation process by asking the local field organization to contact the study participant and/or HCP to gather more necessary information. The field organization then will contact the study participant and/or HCP in the local language. The field organization will provide the medical documentation and an English translation to ZEG Berlin for further processing.

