Under routine medical conditions, diagnosis of a disease/condition is not always confirmed by a diagnostic method with high specificity. Therefore, the primary study outcomes will be classified by ZEG Berlin's medical event validation team according to a predefined algorithm which will be further specified in the working procedures. The data is captured by ZEG Berlin's medical event validation team in the eCRF section for event validation.

- **Definite Event:**
Diagnosis confirmed by diagnostic measures with high specificity or written proof available e.g., medical record.
- **Probable Event:**
Absence of confirmation by a diagnostic measure with high specificity for the diagnosis, but clinical diagnosis confirmed (verbally or in writing) by an HCP or supported by diagnostic tests with low specificity.
- **Possible Event:**
Condition considered as primary outcome was reported by the study participant only and no confirmation could be obtained to prove or disprove the event or no diagnostic measures were performed that could have clarified the diagnosis.
- **Event not confirmed:**
Diagnosis reported by the study participant is excluded by diagnostic procedures.
A different medical condition is diagnosed by the attending HCP.

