5.6 Data management

5.6.1 Databases

During the study, two different types of data will be collected: (I) administrative data, which includes contact details of HCPs and study participants, and (II) study data, which includes all questionnaire data including baseline data and all subsequent follow-up forms. All study data will be collected and managed through the EDC system, MediData Rave [17] and ePRO [9]. For data security and privacy reasons, administrative data are stored separately from the study data (e.g., firewall). Access to administrative data will be restricted and only be accessible for the teams who require contact with the study participants and/or diagnosing/treating HCPs.

Where local regulations permit, the consent and informed consent form (ICF) signing process will occur electronically via the MediData eConsent application. All outcome variables and potential covariates will be entered in standardized eCRFs. After data entry, missing or implausible data will be queried, and the data will be validated by ZEG Berlin's study data management team.

Study data will be entered directly into the ePRO questionnaire by the study participants via MediData. The quality control of entered data will be supported by edit checks which include range, coding, missing and date checks as well as cross-reference (consistency) checks between variables.

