5.10.4 SMAC

The study will be overseen by an independent committee of experts, the SMAC, who will be responsible for regular review and evaluation of collected data during study conduct as well as for the review of the study protocol, statistical analysis plan, interim results, study report, and publications. ZEG Berlin and its research team will be accountable to the SMAC in all scientific matters, with the oversight of Abbott. ZEG Berlin will present all relevant data to the SMAC in a timely fashion. The members of the SMAC are international experts in relevant scientific fields (e.g., Pediatrics, Reproductive Medicine, Obstetrics and Gynecology and Epidemiology). The members will receive remuneration of expenses and an honorarium to compensate for loss of potential earnings during their work for the SMAC. The members will not be involved in or paid for the operational conduct of the study. Members of the SMAC are listed in [Annex 3.1](#).

6 Protection of human subjects

Before collection of any data, a signed ICF and data privacy form is obtained by the participant. ICFs must comply with individual study country law and regulations, including approval from local IEC/IRB.

Participants will sign ICFs at study enrollment after being informed about the study. The eligible participants will be informed about the purpose of the study, the character of the study, timing and content of follow-up contacts, and collection of contact information. Consent will include permission to contact participants and their treating HCP, if required. Participants will be asked to provide personal contact information (e.g., telephone number, home and e-mail address). Participants retain the right to withdraw their consent at any time during the study and without consequences. The ICF will include comprehensive information on processing of personal data according to GDPR.

To comply with rules and regulations regarding the privacy of study participant data, a firewall will be established between the ZEG Berlin central study team and local field organizations team. Members of each team are physically situated in different locations and personal identifiable information (PII) of study participants and HCPs is only seen and handled by the field organizations team situated in each country. Data will be stored on a password protected, secured server and only accessible to authorized users (e.g., field organizations team).

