7 Management and reporting of adverse events/adverse reactions

All baseline and follow-up questionnaires will be completed by the study participant using the ePRO questionnaire. The ePRO questionnaires are sent directly to study participants and do not necessarily follow a defined clinical visit or investigation. This means that information reported by the study participants may have occurred days, weeks, or months prior to the follow-up information being received by ZEG Berlin.

The EDC solution will be programmed to automatically flag questionnaires with a potential AE. These questionnaires will be forwarded to ZEG Berlin's medical event validation team and processed according to the working procedures and the SMP.

All reported and flagged AEs will be assessed by the medical event validation team for seriousness and drug relationship and reported in alignment with relevant pharmacovigilance regulations.

When there is no indication of a possible causal relationship to a drug available from the HCP, the medical event validation team at ZEG Berlin will determine the likelihood of a causal relationship to the above defined medical product subject to the study for each adverse event in accordance with a predefined algorithm (cf. [Annex 3.2](#)) and general medical judgement.

The seriousness of an event will be judged on the basis of the accepted SAE/SADR definition given in ICH-E2A (see GVP Annex IV) by the medical event validation team. The version of the list of Designated Medical Events (DMEs) included as [Annex 4](#) is used to determine further serious cases, whenever none of the ICH-E2A seriousness-criteria are met.

This is an observational registry study where the primary outcome of interest is the assessment of major malformations in the fetus and newborn. The collection of non-serious adverse drug reaction (ADR) data is not foreseen. Dydrogesterone has been available on the market for pregnancy related indications for the last 60 years; dydrogesterone is indicated for early bleeding in pregnancy, recurrent pregnancy loss and IVF/ART support. The adverse event profile of the drug is well established, and the collection of these data will not add to the scientific literature available. Therefore, the other pharmacovigilance relevant information (OPRI) and the following non-serious ADRs will not be collected in this study:

- Nausea
- Abdominal pain
- Vomiting
- Diarrhea
- Dry mouth
- Indigestion
- Rash
- Itching
- Hives/ Urticaria
- Cough

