- Breast swelling

- Depression (unless serious)
- Mood swings
- Trouble falling asleep
- Headache/Migraine
- Dizziness
- Somnolence
- Drowsiness
- Oedema
- Weight gain

All other non-serious ADRs reported will be provided in pseudonymised, tabulated form in the interim study reports, including non-serious ADRs under drugs that are not marketed by Abbott.

Serious adverse drug reactions (SADRs) will be reported via CIOMS-I form to the responsible MAH. In case an event is found to be serious only after the event assessment, a CIOMS-I report will be sent consecutively.

All malformations in fetus/newborns that will be validated and terminations of pregnancy with exposure to a medical drug will be reported to Abbott via CIOMS-I form regardless of their potential relationship to that medical drug and regardless of whether Abbott is the MAH of the drug that the study participant and the fetus were exposed to. The CIOMS-I form will include all available relevant information about the case.

The Safety Management Plan (SMP) shall set forth rules and procedures concerning pharmacovigilance reporting and shall supersede any and all prior pharmacovigilance and safety agreements.

ZEG Berlin will not monitor whether the marketing authorization holders meet their reporting obligations to the Health Authorities according to (inter)national rules.

8 Plans for disseminating and communicating study results

The study protocol and other relevant study materials will be submitted to the appropriate Ethical Committees (incl. the ethics committee of the Medical Association in Berlin, Germany and Data Privacy Officers in Germany). The study will be registered in the public study registry of the U.S. National Institutes of Health's (see <http://clinicaltrials.gov>) and the 'European Network of Centres for Pharmacoepidemiology and Pharmacovigilance (ENCePP) study database (see http://www.encepp.eu/encepp_studies/index.html). ZEG Berlin is planning to receive the ENCePP quality seal for this study.

Furthermore, it is planned to use the analysis dataset for scientific communication (e.g. peer-reviewed publication, conferences). Any publications concerning this study shall abide by the guidelines of the International Committee of Medical Journal Editors (ICMJE). All publications, presentations or other disclosure will be discussed with Abbott prior for submission.

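### One team both classifies the reported major malformations and judges drug relationship, with treatment data in its working system and no masking stated, so confirmation can differ by exposure

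*Protocol*

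**What the plan says.** **Classification.** Section 5.2.3 sends every questionnaire with a potential major malformation to ZEG Berlin's medical event validation team: "The medical event validation team will work within the EDC solution to validate all events considered as a primary study outcome". Events are graded definite, probable, possible or not confirmed by the "medical event validation team according to a predefined algorithm which will be further specified in the working procedures". Where more information is needed, the local field organization approaches the participant or HCP: "The field organization will provide the medical documentation and an English translation to ZEG Berlin for further processing".

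**Drug relationship.** Section 7 names the same team: "All reported and flagged AEs will be assessed by the medical event validation team for seriousness and drug relationship". Where the HCP gives no view on causality, the team "will determine the likelihood of a causal relationship to the above defined medical product subject to the study for each adverse event". Validated malformations with drug exposure also go to the sponsor on a CIOMS-I form, "regardless of their potential relationship to that medical drug and regardless of whether Abbott is the MAH of the drug".

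**Access to treatment data.** Section 5.6.1: "All study data will be collected and managed through the EDC system, MediData Rave". The variables in Section 5.3.2.4 include study treatment, its start and its duration.

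**Separation of information.** The firewall in Section 6 concerns identity: "personal identifiable information (PII) of study participants and HCPs is only seen and handled by the field organizations team". It does not cover treatment. Section 5.10.4 gives the advisory council review of data and reports, but no adjudication of individual cases.

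**The concern.** Judging drug relationship requires knowing the drug: Annex 3.2 relies on the time course of administration and the drug's pharmacology. If the same people grade the primary outcome with exposure in view, their grading may lean one way or the other without intent. The room for this is limited but real. The probable class accepts verbal confirmation by an HCP or tests of low specificity. The possible class depends on whether confirmation could be obtained. Re-contact takes place when it may be necessary, with no uniform rule given. Some listed malformations also need judgement, such as dysmorphic facies or abnormal skin findings.

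The primary claim is non-inferiority on an odds ratio built from these classifications. Under-confirmation on dydrogesterone would favour that claim; under-confirmation in the reference group would work against it. Section 5.9 expects no substantial impact from misclassification and does not discuss assessors' knowledge of exposure. Masking cannot be restored once cases have been graded with treatment known.

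**Working it through.** **1. Does the text put both tasks on one team with access to exposure?**
- Classification: medical event validation team (5.2.3).
- Drug relationship: medical event validation team (7).
- Workplace: the EDC (5.2.3), which holds all study data (5.6.1), including treatment (5.3.2.4).
- Barrier on treatment information: none stated; the Section 6 firewall covers identifiers only.

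The shared team is stated outright. Knowledge of exposure at the moment of grading is an inference, because neither the order of the tasks nor the EDC permissions are given.

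**2. Inputs for the illustration.** From Section 5.5: reference rate 0.02, margin OR 2.0, one-sided alpha 0.025. Effective sizes are 3,136 reference and 1,343 dydrogesterone in cohort A, and 2,059 per group in cohort B. Assumed, not in the protocol: the share of true events confirmed, c1 on dydrogesterone and c0 on reference, with unconfirmed events counted as non-events.

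**3. The plan's own figures.** The 20% drop-out inflation reproduces: 3,136/0.8 = 3,920; 1,343/0.8 = 1,679; 2,059/0.8 = 2,574. The effective sizes give about 87% power in an unadjusted score test (simulated 87.3% in A and 87.1% in B) rather than the stated 90%. That is a separate matter; 87% serves here only as the baseline.

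**4. Under-confirmation on dydrogesterone, true OR 2.0.**
- Reference odds: 0.02/0.98 = 0.020408.
- Dydrogesterone odds: 2 × 0.020408 = 0.040816, so the risk is 0.040816/1.040816 = 0.039216.
- With c1 = 0.90 and c0 = 1: 0.90 × 0.039216 = 0.035294; odds 0.035294/0.964706 = 0.036585.
- Observed OR: 0.036585/0.020408 = 1.79.

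The chance that the upper limit falls below 2.0 is Φ[(ln 2.0 − ln OR)/SE − 1.96], with SE² = 1/(n1·p1·(1−p1)) + 1/(n0·p0·(1−p0)). In cohort A, SE = 0.195 and (0.6931 − 0.5837)/0.195 = 0.56, so Φ(−1.40) = 8.1%. In cohort B, SE = 0.198 and the result is 8.0%. Simulated score tests agree:

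| c1 / c0 | Observed OR | False non-inferiority, A | B |
|---|---|---|---|
| 100% / 100% | 2.00 | 2.4% | 2.7% |
| 95% / 100% | 1.90 | 4.5% | 4.8% |
| 90% / 100% | 1.79 | 8.0% | 8.4% |
| 80% / 100% | 1.59 | 20.6% | 21.4% |

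**5. Reverse direction, true OR 1.0.** With c1 = 1 and c0 = 0.90, the reference risk is seen as 0.018, with odds 0.018/0.982 = 0.018330. Observed OR: 0.020408/0.018330 = 1.11. Power falls from about 87% to 72%.

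**6. How many decisions would tip a null result?** At 2% in both groups, cohort A expects about 27 dydrogesterone events (1,343 × 0.02) and 63 reference events (3,136 × 0.02). Wald upper limits:
- 27 versus 63: 1.58
- 30 versus 63: 1.73
- 36 versus 63: 2.03

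Crossing 2.0 takes nine extra dydrogesterone cases. In cohort B, starting from 41 versus 41, it takes 14.

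**The case against.** The strongest reply is that the scope for judgement is small. Definite events rest on high-specificity diagnostics or written proof. Not confirmed requires exclusion by diagnostic procedures or a different diagnosis by the attending HCP. The malformation list and the grading algorithm are predefined, and consent to contact all treating or diagnosing HCPs is an inclusion criterion. A shift among definite, probable and possible changes the OR only if some of those classes are left out of it. The working procedures and the Safety Management Plan are not shown and may already separate or mask the two tasks. All of this stands. It limits the concern to the less documented cases and to re-contact, and it means the illustration assumes a loss of cases that may never occur.

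It does not remove the point. The protocol fixes both tasks on one team inside a system that holds exposure, and commits to no safeguard. Who grades the primary outcome, and with what knowledge, is a matter of study conduct that belongs in the protocol.

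Two stronger readings are tempting, and neither is supported:
- **A handful of reclassified cases could change the verdict.** From a null result it takes nine in cohort A and 14 in cohort B (step 6). Fewer would decide only if the result already lay near the margin. The 8% figure belongs to a true OR of 2.0, where cohort A expects about 53 dydrogesterone events (1,343 × 0.0392), not 27.
- **The team chooses how hard to chase records by treatment.** Section 5.2.3 says only that re-contact may be needed and that the field organization carries it out.

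**Conclusion.** The point holds as a risk of differential confirmation, of unknown size and direction; it is not a demonstrated bias. The shared team and its place in the EDC are stated in the protocol. That graders will know the exposure follows from those statements unless documents not shown prevent it. If confirmation differed by ten percentage points against dydrogesterone cases, a true OR of 2.0 would be seen as 1.79 and false non-inferiority would be about 8% instead of 2.5%. With the same gap in the other direction, a true OR of 1.0 would be seen as 1.11 and power would be 72% instead of about 87%. Both results rest on assumed confirmation shares, on unconfirmed events being counted as non-events, and on an unadjusted analysis at the Section 5.5 effective sizes. The change is worth making because it is cheap and cannot be made after the cases have been graded.

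**What to change.** State in Section 5.2.3 that:
- outcome class and major/not-major status are assigned and locked by members of the medical event validation team who are masked to treatment;
- these members use a restricted EDC view without treatment fields, since redacted documents alone do not mask someone with full EDC access;
- the field organization removes treatment details from the records while translating them;
- the same retrieval and re-contact steps apply to every report.

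State in Section 7 that other existing team members do the drug-relationship assessment and safety reporting on its own timeline, so that reporting never waits for the masked grading. If the working procedures already provide for this, a sentence pointing to them is enough.

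Cost: some handling time and EDC set-up, but no new assessors and no change to sample size or participant burden. Masking will be incomplete where a record reveals the treatment in its narrative.

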5.3 Definition of outcome parameters

5.3.1 Definition major malformations

Malformations of primary interest are:

Congenital malformation	
Central nervous system	Respiratory system
Agenesis of the corpus callosum Arhinencephaly / Holoprosencephaly Hydranencephaly Hydrocephaly Macrocephaly Meningoencephalocele Microcephaly Neural tube defect (anencephaly, spina bifida, craniorachischisis) Porencephaly Syringomyelia	Branchial cleft cyst Congenital cystic malformation Larynx hemangioma Pulmonary hypoplasia
Head and neck	Digestive system
Oral Cleft palate without cleft lip Cleft lip with or without cleft palate Eye Anophthalmos Ankyloblepharon Dacryostenosis Ectropion / Entropion Epibulbar dermoid Exophthalmos congenital Glaucoma Nystagmus Persistent Hyperplastic Primary Vitreous Other Anotia/microtia Choanal atresia Congenital hearing loss/disorder	Annular Pancreas Anorectal atresia / stenosis Bile duct atresia Diaphragmatic hernia Esophageal diverticulum Imperforate anus Hepatomegaly Hirschsprungs disease Intestinal Malrotation Microcolon Meconium ileus/plug Obstruction by fibrous band Oesophageal atresia / stenosis Persistent omphalomesenteric duct Pyloric stenosis Pylorospasm

Dysmorphic facies Facial palsy/asymmetric crying facies Hemifacial microsomia Macroglossia Potter facies Torticollis	Rectovaginal fistula Small intestine atresia / stenosis Splenomegaly Tracheo-oesophageal fistula
Cardiovascular system	Skin
All congenital cardiovascular malformations are of interest, excluding : Heart murmur Systolic murmur Haemangioma The following three events will be evaluated at the interim analysis, and if these are still of primary interest further evaluations will be undertaken: Persistent Atrial septum defect Persistent Patent foramen ovale Persistent Patent ductus arteriosus	Abnormal skin findings, excluding : Hyperpigmented/ hypopigmented macules Scars / lesions Skin tags Ichthyosis
Urinary system	Reproductive system
Bladder/urethral diverticulum Congenital cystic kidney disease Enlarged kidney Hydroureter/hydronephrosis Hypospadias Other congenital bladder anomaly Patent/persistent urachus Prolapsed bladder Prune belly Renal agenesis Renal (hypo)dysplasia Renal stones Vesicoureteral reflux	Cliatoromegaly Cryptorchism Ovarian cysts Epispadias Hermaphroditism Small penis Torsion of testis Pseudohermaphroditism Other congenital genitourinary abnormality
Musculoskeletal system	Genetic / chromosome
Abnormal palmar/plantar creases Arthrogryposis Bowed long bones / missing bones Congenital foot malformation Congenital hand malformation Craniosynostosis Genu valgum/genu varum Hip dislocation/Hip dysplasia Joints in abnormal positions Kinematic imbalances due to suboccipital strain (KISS) Limb reduction defects Pectus abnormalities Polydactyly Scoliosis without vertebral anomalies Sprengel deformity Syndactyly Various head shape abnormalities (Ex: plagiocephaly) without craniosynostosis	Down syndrome Genetic syndromes + microdeletions Klinefelter syndrome Trisomy 13 Trisomy 18 Turner's syndrome
	Other
	Amniotic bands Aplasia Ascites/Anasarca/Hydrops Cysts of various organs Cystic lymphangioma Gastroschisis Hemihyperplasia/ hemihypertrophy Inguinal hernia Lymphangiectasias Multiple congenital abnormalities Omphalocele Situs inversus

These listed malformations will be identified during follow-up, i.e., major malformation in the fetus, and after delivery, i.e., major malformation diagnosed in newborns (i.e., pre- and postnatally diagnosed malformations).

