5.3.2 Variables

5.3.2.1 Variables to determine the primary objective

- Rate of major malformations (as defined in section 5.3.1.) in fetus and newborn

- Prescribed treatment in first trimester for each indication
- Indication of use
- Risk factors and potential confounders as per section 5.3.2.4.

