5.7.3 Interim analysis

There are 3 interim analyses planned during the study conduct. It is planned to have the interim/progress reports developed on an annual basis by ZEG Berlin, with the oversight of Abbott. The content of the interim/progress reports should follow a logical sequence and should include all the available data that are judged relevant for the progress of the study, for example, number of subjects who have entered the study, number of exposed subjects or number of subjects presenting the outcome of interest, problems encountered and deviations from the expected study plan.

The interim reports generated from interim analysis will inform the advisory board, regulatory authorities, the funders, and the investigator team about preliminary results, and whether incidence assumptions regarding exposure as basis for the sample size calculation are realistic. Details on the interim analysis will be explicitly described in the SAP. The interim analyses planned for this study are of a descriptive nature and will not allow for adaptation of the study design. However, if a potential (safety) issue is identified during the study, in depth review will be made in collaboration with the SMAC, with the oversight of Abbott and thereafter, any actionable items will be undertaken.

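### Section 5.3.1 leaves it to an unspecified interim analysis whether three cardiac diagnoses stay in the primary outcome, so the endpoint can be set after outcome data by treatment are seen

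*Protocol*

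**What the plan says.** All references are to the protocol.

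- Section 5.3.1 opens its table with "Malformations of primary interest are". Section 5.3.2.1 makes that table the primary variable: "Rate of major malformations (as defined in section 5.3.1.) in fetus and newborn".
- The cardiovascular cell begins "All congenital cardiovascular malformations are of interest" and excludes heart murmur, systolic murmur and haemangioma. The three diagnoses are not among the exclusions. They are set apart with the sentence "The following three events will be evaluated at the interim analysis, and if these are still of primary interest further evaluations will be undertaken".
- Section 5.7.3: "There are 3 interim analyses planned during the study conduct". The milestones put the reports in March 2022, December 2022 and September 2023. The reports bring preliminary results to the advisory board, authorities, funders and investigator team. Examples of content are the numbers of exposed subjects and of subjects with the outcome.
- The same section adds: "The interim analyses planned for this study are of a descriptive nature and will not allow for adaptation of the study design". It refers further interim detail to the SAP.
- Section 5.2.3, on outcome classification: "The medical event validation team will work within the EDC solution to validate all events considered as a primary study outcome". Section 7, on adverse events: "All reported and flagged AEs will be assessed by the medical event validation team for seriousness and drug relationship".

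**The concern.** A primary endpoint should be settled before anyone can see how its components fall by treatment. Here three components stay or go at an interim look in an open, observational study, and the protocol does not keep treatment-specific data from whoever decides.

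These are not incidental components. Section 3 cites a suggested excess of major cardiac malformations (from a study since retracted) among the questions that led to the registry. A finding of no excess risk is open to challenge if cardiac diagnoses could have been removed after their distribution was known.

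A secondary and separate matter is that one team both classifies primary outcomes and judges drug relationship, and the protocol does not say in which order.

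**Working it through.** **1. The two clauses.** Section 5.3.1 makes continued primary interest depend on an interim evaluation. Section 5.7.3 says that interims are descriptive and change nothing in the design. Which events make up the primary outcome is part of the design, so both cannot hold. Section 5.3.1 speaks of one interim analysis; section 5.7.3 plans three.

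**2. Which look could decide.** Milestones (section 2): first patient December 2021, last follow-up April 2024. Assumptions: mid-December start, month-end looks, uniform recruitment, entry at 6-12 weeks, due date at 40 weeks, FU2 6-12 weeks after it.
- Shortest lag from entry to FU2: 46 − 12 = 34 weeks (7.8 months). Longest: 52 − 6 = 46 weeks (10.6 months).
- Recruitment window: 28.5 − 7.8 = 20.7 months, or 28.5 − 10.6 = 17.9 months.
- Interim 1 (3.5 months): no FU2 data.
- Interim 2 (12.5 months): 1.9/17.9 = 11% to 4.7/20.7 = 23% have reached FU2.
- Interim 3 (21.5 months): 10.9/17.9 = 61% to 13.7/20.7 = 66%.

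Only the third look holds much postnatal information. It lies inside the 50-75% range used below.

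**3. The plan's own figures (section 5.5).** Rate 0.02 in both groups, margin OR 2.0, one-sided alpha 0.025, power 90%. Effective sizes (reference + dydrogesterone) are 3,136 + 1,343 in cohort A and 2,059 + 2,059 in cohort B. The drop-out inflation reproduces: 3,136/0.8 = 3,920; 1,343/0.8 = 1,679; 2,059/0.8 = 2,574. The 90% does not quite: an odds-ratio score test gives 86.5% (A) and 86.3% (B) by approximation, or 87.3% and 87.1% exactly. This may reflect the software's algorithm and does not affect the point.

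**4. Error if the choice follows the treatment comparison.** The protocol gives no rate for the three diagnoses, so their share is assumed: 20-60% of a 2% total. True OR is 2.0 for every event. Non-inferiority is declared if log OR + 1.96·SE < ln 2, with SE² = 1/a + 1/b + 1/c + 1/d over the four cells. The three events are kept or dropped at 50-75% of the data, whichever gives the lower interim OR (400,000 simulated studies per setting).

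| | Definition fixed | Chosen by interim OR |
|---|---|---|
| Cohort A | about 2.1-2.3% | about 2.9-3.2% |
| Cohort B | about 2.4-2.8% | about 3.4-3.8% |

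Score-test versions with shares of 30-50% gave 3.2-3.7% when the three diagnoses came on top of a 2% rate. Within a 2% total they gave 3.5-4.1% (A) and 3.8-4.4% (B).

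**5. Error if the choice uses pooled counts only.** With a score test and shares of 30% and 50%, the error was 2.5-2.6% (A) and 2.7-2.8% (B). The fixed definitions gave 2.4-2.9%, so there is no material inflation.

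**6. Harm confined to the three diagnoses.** Assume OR 3 for these and OR 1 for the rest. The composite OR is roughly share × 3 + (1 − share) × 1.

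| Share | Composite OR | Non-inferiority declared, always counted (A / B) | Inclusion follows interim OR (A / B) |
|---|---|---|---|
| 50% | 0.5×3 + 0.5×1 = 2.0 | 2.2% / 2.6% | 56% / 60% |
| 60% | 0.6×3 + 0.4×1 = 2.2 | 0.6% / 0.7% | 46% / 52% |

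Hand check, cohort B, 60% share: the other events occur at 0.8%, so 0.008 × 2,059 = 16.5 per group. SE = √(2/16.5 + 2/2,042.5) = 0.350, and 0.693/0.350 − 1.96 = 0.02, which is a probability of about 51%. The last column is therefore close to what the remaining events give alone: the interim rule drops the three diagnoses almost every time.

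**7. Power.** With no true difference, dropping the three diagnoses when they are 20/40/60% of a 2% rate lowers power to 78/66/49% (A) and 79/68/52% (B). If they come on top of 2% and add 0.5-2 points, power is 93-99% (A) and 92-99% (B). Membership matters even without selection.

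**The case against.** - **Results by treatment are not promised.** A reader might infer that the decision will be made on treatment-specific results. The protocol does not say so. Section 5.7.3 lists exposed subjects and subjects with the outcome, not outcomes by exposure, and the SAP, not shown here, could set a pooled or masked rule. This stands: the text shows that the endpoint can be set this way, not that it will be. It does not remove the conflict between two sections of the protocol itself.
- **The clause may mean only further case work-up.** The stated consequence is further evaluation, not removal. But continued primary interest, under a heading that lists the malformations of primary interest, is most naturally about membership. If only work-up is meant, the sentence needs rewording.
- **The inflation is a worst case.** It needs an assumed event share and a choice by the better treatment comparison, and it vanishes under pooled counts. This stands. The rise is about one percentage point when every component carries the same OR. The figures in step 6 add a further assumption, OR 3 confined to these diagnoses. They show the effect of exclusion, which a composite fixed in advance without the three would share. The difference is that such an exclusion would have been declared before the data.
- **The first interim is harmless.** With no FU2 data in March 2022, a decision then could not rest on postnatal findings by treatment. True, but the protocol does not say that the first look decides.
- **The classifying team may not see exposure.** One might conclude that it does, because it also judges drug relationship. The protocol shows only that one team does both. It gives neither the order nor the visible fields, and it refers to a predefined classification algorithm. Exposure-aware classification is possible, not stated.

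**Conclusion.** The point holds. As written, section 5.3.1 leaves part of the primary endpoint to an unspecified interim look, against section 5.7.3, and nothing in the protocol keeps data by treatment from those who decide.

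The size depends on conduct. Selection on the interim treatment comparison moves the one-sided error from about 2-3% to about 3-4%. Selection on pooled data leaves it essentially unchanged. Harm confined to the three diagnoses could be missed about half the time or more under the assumptions in step 6. The share of events, the timing and the selection rule are all assumptions; the protocol gives none of them.

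The documents do not support saying that the sponsor intends to choose by result, that interim tables are split by treatment, or that outcome classification is made with exposure known. Classification bias cannot be sized from the protocol, and the main conclusion does not rest on it.

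**What to change.** 1. Delete the interim clause in section 5.3.1.
2. State there, before any outcome data by treatment are reviewed, whether the three diagnoses count in the primary composite. Define persistence from what the study already obtains: diagnosis date and diagnostic test (section 5.3.2.4) and the validation documents (sections 5.2.3 and 5.4). Apply it identically to all treatment groups. A definition that needs a particular examination at a set age would not suit this study, because no such examination is scheduled and only infants who happened to have it could count.
3. Report the composite with and without the three diagnoses, whatever the interims show. This also keeps the cardiac question visible if they are left out.
4. If an interim decision is kept, name the interim and the criterion, use only data pooled over treatment, and have it made by persons without access to exposure.
5. Separately, complete and lock the definite/probable/possible/not confirmed classification before the drug-relationship assessment, with treatment fields hidden where feasible.

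Cost: protocol wording, one additional reported analysis, a view restriction in the EDC system and slightly slower case processing. No extra participants or staff are needed. The change is credible only if made before results by treatment have been seen.
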